**Appendix A: Enrollment Eligibility Checklist**

IRB Protocol No.		WFBCCC Protocol No.	62718
Study Title: A Randomized Trial of Consolidative Immunotherapy with vs without Thoracic Radiotherapy and / or Stereotactic Body Radiation Therapy (SBRT) after First-line Systemic Therapy for Metastatic NSCLC			
Principal Investigator: [name].			

**ENROLLMENT**

- Patients are eligible for enrollment if they have metastatic NSCLC and have undergone at least 4 cycles of upfront standard of care systemic therapy. Patients must have a CT chest abdomen pelvis (ideally with IV contrast) performed after the point of completion of 4 cycles of standard of care systemic therapy, but no later than 180 days from the first day of systemic therapy. This CT scan must be completed within 180 days of the first day of systemic therapy, and must demonstrate no evidence of disease progression per RECIST v1.1.
- Patients may start their standard of care maintenance immunotherapy at the discretion of their treating medical oncologist prior to enrollment. Patients must be enrolled AND randomized no later than 180 days from the first day of cycle 1 of standard of care systemic therapy. The first day of cycle 1 of systemic therapy is considered day # 1. At most, an additional 179 days may elapse from this point to remain eligible for inclusion on this study.

**RANDOMIZATION**

- Once enrolled, patients will have a restaging PET/MRI brain (*exceptions below*)  
 If restaging scans demonstrate  $\leq$  eight sites of non-progressive active residual disease, then patients are eligible for randomization. If restaging scans demonstrate progression of disease, then these patients will not be eligible for randomization, but will be followed by their primary medical oncologist or radiation oncologist every 3 months for overall survival only.

*\* If a PET has been performed within 30 days of enrollment with no evidence of progression per RECIST v1.1, then this scan may be used and does not have to be repeated prior to randomization*

*\* If an MRI brain has been performed within 90 days of enrollment with no evidence of progression per RECIST v1.1, then this scan may be used and does not have to be repeated prior to randomization*

- Randomization should occur within 21 days of enrollment.
- Once randomized, protocol directed therapy should occur within 21 days from randomization (ie. start of consolidative RT or resumption of maintenance immunotherapy)

**If randomized to consolidative radiation therapy then maintenance immunotherapy:**

Maintenance immunotherapy may NOT be delivered concurrently with consolidative radiation. Concurrently is defined as on the same day of any radiation treatment or on any day between the first and last treatment of radiation. Resumption of maintenance immunotherapy after completion of radiation therapy is at the discretion of the treating medical oncologist. They may resume maintenance immunotherapy as early as 24 hrs after the last radiation treatment, but resumption should be no later than 8 weeks from the last radiation treatment. If treatment related toxicities prohibit administration of maintenance immunotherapy, then restarting this therapy is at the discretion of the treating medical oncologist. In such cases, patients will remain on study until they experience progression or death. If they experience progression, patients will be followed for overall survival only per appendix L past the point of progression.

**If randomized to continued maintenance immunotherapy alone:**

Patients will begin or resume maintenance immunotherapy no later than 21 days following randomization.

A Randomized Trial of Consolidative Immunotherapy with vs without Thoracic Radiotherapy and / or Stereotactic Body Radiation Therapy (SBRT) after First-line Systemic Therapy for Metastatic NSCLC  
 Wake Forest Baptist Comprehensive Cancer Center  
 WFBCCC # 62718

Inclusion Criteria (as outlined in study protocol section 3.0) Must answer yes to all questions below, otherwise patient is not eligible	Criterion is met	Criterion is NOT met	Source Used to Confirm * Document dates and lab results
18 years or older			
Performance Status 0-2 (ECOG) at time of consult with radiation oncology			
Pathologically proven NSCLC with evidence of metastatic disease			
Must have received 4 cycles of standard of care systemic therapy, with a CT chest abdomen pelvis that was performed after completion of these 4 cycles and demonstrates no evidence of progression per RECIST v1.1			
To be eligible for enrollment and randomization, patients must be within 180 days from their first dose of systemic therapy. Cycle 1 day 1 is defined as day 1. If enrolled on day 180, the patient would need to be randomized the same day.			
Persistent active disease must be amenable to radiation treatment per the treating radiation oncologist, and patients must have at least one residual site of disease which can be identified by CT or PET/CT and targeted with radiation.			
Patients who previously had earlier stage NSCLC treated definitively and have now developed new distant disease, are eligible for inclusion if they have undergone at least 4 cycles of chemo-immunotherapy for their metastatic recurrence, and they meet all criteria above.			
There are no strict size or tumor number limitations in a given organ (lung, liver, abdomen pelvis, or spine). This is at the discretion of the treating radiation oncologist.			
Exclusion Criteria (as outlined in study protocol)	Criteria NOT present	Criteria is present	Source Used to Confirm *
More than 180 days has elapsed since day 1 of cycle 1 of systemic therapy.			
Pregnant or lactating women			
The patient has received treatment for other carcinomas within the last three years (Except for cured non-melanoma skin cancer, low-risk prostate cancer, T1/T2 glottic cancer, stage 0 or stage I breast cancer, non-invasive bladder cancer, or treated in-situ cervical cancer). Prior lung cancer diagnosis now with oligometastatic recurrence is not an exclusion criteria.			
Patients with major activating mutations in EGFR (del19, L858R, and T790M) or ROS 1 or ALK gene rearrangements are excluded			
Patient eligibility for immunotherapy is at the discretion of the treating medical oncologist. Immunologic conditions including Lupus, rheumatoid arthritis, psoriasis or other conditions requiring immune suppression are NOT strict exclusions			

This subject is  eligible /  ineligible for enrollment in this study.

OnCore Assigned PID: \_\_\_\_\_  
 Signature of research professional confirming eligibility: \_\_\_\_\_  
 Date: \_\_\_\_ / \_\_\_\_ / \_\_\_\_ (MM/DD/YYYY)

Signature of Treating Physician: \_\_\_\_\_  
 Date: \_\_\_\_ / \_\_\_\_ / \_\_\_\_ (MM/DD/YYYY)

Signature of Principal Investigator\*\*: \_\_\_\_\_  
 Date: \_\_\_\_ / \_\_\_\_ / \_\_\_\_ (MM/DD/YYYY)

\* Examples of source documents include clinic note, pathology report, laboratory results, etc. When listing the source, specifically state which document in the medical record was used to assess eligibility. Also include the date on the document. Example: "Pathology report, 01/01/14" or "Clinic note, 01/01/14" \*\*Principal Investigator signature can be obtained following registration if needed

A Randomized Trial of Consolidative Immunotherapy with vs without Thoracic Radiotherapy and / or Stereotactic Body Radiation Therapy (SBRT) after First-line Systemic Therapy for Metastatic NSCLC  
Wake Forest Baptist Comprehensive Cancer Center  
WFCCC # 62718

**Appendix B: Protocol Registration**

DEMOGRAPHICS	
Patient: Last Name: _____	First Name: _____
MRN: _____	DOB ____/____/____ (MM/DD/YYYY)
ZIPCODE: _____	
SEX:  Male  Female	Ethnicity (choose one):  Hispanic  Non-Hispanic
Race (choose all that apply):  WHITE  BLACK  ASIAN  PACIFIC ISLANDER  NATIVE AMERICAN	
Height: _____.____ inches	Weight: _____.____ lbs.(actual)
Surface Area: _____.____ m 	
Primary Diagnosis: _____	
Date of Diagnosis: _____._____._____._____._____._____. (MM/DD/YYYY)	
Performance Status: ____ ECOG	
PROTOCOL INFORMATION	
Date of Registration: _____/_____/_____ (MM/DD/YYYY)	
MD Name (last) : _____	
Date protocol treatment started: _____/_____/_____	
Informed written consent:  YES  NO	
(consent must be signed prior to registration)	
Date Consent Signed: _____/_____/_____	
PID # (to be assigned by OnCore): _____	

*Protocol Registrar can be contact by calling [contact] between 8:30 AM and 4:00 PM, Monday – Friday.  
Complete the eligibility checklist in WISER and then give the completed Eligibility Checklist and Protocol Registration Form must be hand delivered, faxed or e-mailed to the registrar at [contact] or [[contact]](mailto:[contact]), respectively.*

**Appendix C: Eligibility for Randomization**

Randomize within 21 days of enrollment

OnCore Assigned PID: \_\_\_\_\_

This subject is  eligible /  ineligible for randomization in this study.

Signature of research professional confirming eligibility for randomization : \_\_\_\_\_  
Date: \_\_\_\_/\_\_\_\_/\_\_\_\_ (MM/DD/YYYY)

Signature of Treating Physician: \_\_\_\_\_

Date: \_\_\_\_/\_\_\_\_/\_\_\_\_ (MM/DD/YYYY)

Signature of Principal Investigator\*\*: \_\_\_\_\_

Date: \_\_\_\_/\_\_\_\_/\_\_\_\_ (MM/DD/YYYY)

**Appendix D: Numbering Sites of Disease**

Completed prior to randomization by the treating radiation oncologist

How many total active sites of persistent disease are present after PET/MRI restaging \_\_\_\_\_

Location and number of extracranial disease sites to be treated  
\_\_\_\_\_

CNS lesions (Y/N) \_\_\_\_\_ managed w resection/SRS \_\_\_\_\_ (Y/N)  
Signature \_\_\_\_\_ Date \_\_\_\_\_

**Appendix E: Radiotherapy Technical Parameters**

**Radiotherapy Technical Parameters/Data Collection Form completed by the treating radiation oncologist**  
The following information will be collected for **EACH** extra cranial tumor treated with radiation

Tumor Location (side/lobe if applicable):		
Dose Prescribed (Gy):		
Total number of fractions:		
Treatment volumes (cm  ):	GTV:	PTV:
% PTV receiving prescribed dose:		
Volume of isodose for 50% prescription dose:		
Volume of isodose for 100% prescription dose:		
Was the plan 3D, VMAT, or IMRT?		

A Randomized Trial of Consolidative Immunotherapy with vs without Thoracic Radiotherapy and / or Stereotactic Body Radiation Therapy (SBRT) after First-line Systemic Therapy for Metastatic NSCLC  
Wake Forest Baptist Comprehensive Cancer Center  
WFBCCC # 62718

**Appendix F: 30-day Treatment Follow-up Form**

Definition of 1 mo. or 30 day followup

1. For patients randomized to RT, this time point is considered 30 days +/- 14 days from end of all radiation therapy treatments
2. For patients randomized to immunotherapy alone, this time point is considered 30 days +/- 14 days from the end of the 2nd cycle of on protocol maintenance immunotherapy

Study Number: \_\_\_\_\_ PID: \_\_\_\_\_

Investigator: [name] M.D. Date: \_\_\_\_ / \_\_\_\_ / \_\_\_\_ (MM/DD/YYYY)

**Instructions:** Complete this form to follow-up with patients for adverse events.

**Name of Person Competing form** \_\_\_\_\_

**Did the subject have any adverse events in the last 30 days?** Yes  No

If yes, please report on AE log in WISER

(Note\*: If an SAE occurs in this period, report the event as required in Appendix S):

**Was the subject removed from the study?** Yes  No

If yes, complete the Off-Study Form

**Did the subject withdraw from the study?** Yes  No

If Yes, complete the Withdrawal of Consent Form

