## 6.0 Pembrolizumab

In order to maintain dose-intensity and cumulative dose-delivery, reasonable efforts should be made to minimize dose reductions and treatment delays. Any subject whose treatment is delayed should be evaluated on a weekly basis until adequate hematologic and non-hematologic parameters have been met. Patients may elect to delay doses of maintenance treatment for up to 3 weeks due to personal preference and this will not constitute a protocol deviation.

Toxicities may require the dose reduction of one or more of the study required medications. The investigator will carefully assess all treatment associated toxicities and, whenever possible, determine if the toxicities can reasonably be attributed to a single agent or a causal relationship with one of the agents can reasonably be ruled out. If appropriate, dose reductions should not affect the dose of other products.

CTC-AE measures will occur at each cycle of consolidation immunotherapy. Dose modifications and treatments for adverse events will be managed at the discretion of the treating physicians per their standard practice. Guidance statements regarding dose modifications and ae management are provided as suggestions for treating physicians but are not mandatory. Reasons for dose delays, dose modifications, or addition of steroid treatments must be documented by the treating physician.

- Toxicity grades are defined using the National Cancer Institute Common Terminology Criteria for Adverse Events (NCI-CTCAE) version 5.0
- Dose escalations are not allowed

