### 7.2 Radiotherapy Dose and treatment methods

The total dose will be flexible based on the judgment of the treating radiation oncologist to respect normal tissue tolerances. Guidelines for suggested normal tissue constraints are listed below in section 7.6. Meeting these constraints are recommended, but not required for inclusion on the protocol. **Ultimately, dose selection is at the discretion of the treating radiation oncologist.** In general, for lung, liver, axial skeleton, and adrenal tumors, a dose of either 54 Gy in 3 fractions (fxs) or 5000 cGy in 5 fx using SBRT techniques will be appropriate if the GTV measures less than 5 cm. For tumors in these organs that are larger than 5 cm, or where normal tissue constraints are grossly exceeded, a dose of 3000-6000 cGy in 10 – 15 fractions may be more appropriate instead. In the case of an untreated primary with involved mediastinal lymph nodes, fractionated radiotherapy over the course of 30 – 33 treatments with or without concurrent chemotherapy may be necessary at the discretion of the treating physician and this is allowed.

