  - c. The schedule above is standard of care for imaging followup. Should a patient be enrolled after starting maintenance immunotherapy and after their first 3 month followup scan, then they may be allowed to switch to 6 months interval imaging at 3yrs from the end of chemo-immunotherapy, rather than a full 3 yrs from the date of randomization in accordance with standard of care. At discretion of treating oncologist.
7. Definition of 1 mo. or 30 day followup
  - a. For patients randomized to RT, this time point is considered 30 days +/- 14 days from end of all radiation therapy treatments
  - b. For patients randomized to immunotherapy alone, this time point is considered 30 days +/- 14 days from the end of the 2nd cycle of on protocol maintenance immunotherapy
8. Two tubes of whole blood may be collected at time of registration or any time prior to initiating any protocol directed therapy and at the 1 month follow up +/- 2 weeks.
9. If patients progress and are not eligible for randomization, or if they progress at any point on the study, they are only followed w appendix L for survival after the point of progression

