**FOLLOWUP VISITS AND CT SCANS HAVE A FLEXIBILITY WINDOW OF +/- 8 WEEKS AROUND THE TIME POINT LISTED ON THE STUDY CALENDAR**

## 8.2 Study Activities – Required Evaluations

- 8.2.1** A medical history, physical examination, weight, NCI comorbidities, and assessment of ECOG performance status within 12 weeks of enrollment. ECOG status will be documented at time of the radiation oncology consult in the electronic medical record.
- 8.2.2** A CT chest abdomen pelvis demonstrating no evidence of progression per RECIST v1.1 that has been performed after completion of 4 cycles of chemo-immunotherapy but no later than 180 days from the first day of chemo-immunotherapy.
- 8.2.3** A PET/CT and MRI brain will be performed, either prior to randomization or a PET that is within 30 days of enrollment, or MRI brain within 90 days of enrollment may be used for purposes of randomization.
- 8.2.4** Biopsy or cytology demonstrating a diagnosis of non-small cell lung carcinoma.
- 8.2.5** Two tubes of whole blood will be collected via routine blood draw and saved for future exploratory biomarker studies as listed on the study calendar, at time of registration and at the 1 month follow up +/- 2 weeks. For radiation patients this is 1 month after the last treatment of radiation. For immunotherapy only patients, this is 1 month after the second dose of maintenance immunotherapy on study.
- 8.2.6** Serum or urine pregnancy test within 1 week of RT in women of child bearing potential.

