More common (>10% of patients): 
 
Temporary, difficulty, pain, or a burning sensation when swallowing
 
Temporary fatigue
 
Tanning, redness of the skin, and hair loss within the treatment area, Skin in the treatment area may remain permanently dry
 
chest hair may not grow back
 
Decrease in blood counts while undergoing treatment causing bleeding, and bruising
 
Cough and some difficulty in breathing due to lung damage
 
	Less common (<10% of patients): 
 
Narrowing of the esophagus causing difficulty swallowing (rarely requiring internal dilation or a feeding tube)
 

Rare but serious (late) (<1% of patients)	

 
Pericarditis – irritation of the heart sac causing a rapid heart rate, or chest pain.
 
Myocarditis – irritation of the heart muscle causing shortness of breath, chest pain, or permanent heart muscle damage
 
Transverse myelitis – irritation of the spinal cord causing weakness or paralysis
 
Bleeding from the airway
 
Narrowing of the airway causing shortness of breath
 
	

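### No toxicity grading is scheduled during radiation, and at the nominal one-month visit the Appendix F 30-day question reaches back only to the last fraction

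*Combined protocol and SAP*

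**What the plan says.** Three parts of the plan schedule toxicity questions around radiation.

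- **Study calendar (section 8.1).** The toxicity row, graded by CTCAE v5.0, is marked at enrollment, at one month, and at the three-monthly and six-monthly visits. There is no column for the radiation course. Footnote 7 places the one-month visit for this arm: "this time point is considered 30 days +/- 14 days from end of all radiation therapy treatments".
- **Per-cycle grading (section 6.0).** "CTC-AE measures will occur at each cycle of consolidation immunotherapy". The radiation-arm paragraph of section 3.0 forbids immunotherapy on any day from the first to the last fraction. It allows resumption from 24 hours to 8 weeks after the last one.
- **Appendix F**, due at one month. It repeats the timing for the radiation arm and asks "Did the subject have any adverse events in the last 30 days". For controls the visit falls "30 days +/- 14 days from the end of the 2nd cycle of on protocol maintenance immunotherapy".

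Appendix J is also due at one month and at each later follow-up. Its item 3 concerns delayed radiotherapy complications since the previous visit, and a yes leads to the adverse event form. Appendix R requires all adverse events to be entered in the institution's system.

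On course length, section 7.2 describes SBRT in 3 or 5 fractions and 10 to 15 fractions for larger tumors. For an untreated primary with involved mediastinal nodes it allows "fractionated radiotherapy over the course of 30" to 33 treatments.

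**The concern.** Objective 2.2.3 is to evaluate the toxicity that radiation adds, and it names esophagitis, dermatologic toxicity and nausea among others. Section 14.2 undertakes to report acute as well as late toxicity. Section 9.1 lists effects of fractionated chest radiation expected in more than 10% of patients. They include temporary painful swallowing, skin redness and "Decrease in blood counts while undergoing treatment causing bleeding, and bruising". Effects of this kind can begin and settle before a visit a month after the last fraction.

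If the scheduled question at that visit does not reach back over the course, such events enter the data only when someone volunteers them. Controls are graded at every three-week cycle over the same calendar period. The difference in ascertainment runs one way: it would make radiation look better tolerated than it is.

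**Working it through.** The plan states no figure for this point, so there is none to reproduce. The check compares two windows.

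**Inputs.** Look-back of 30 days (Appendix F). Visit on day v, where v = 30 - 14 = 16 at the earliest, 30 nominally and 30 + 14 = 44 at the latest (Appendix F; section 8.1, footnote 7). Courses of 3 to 33 fractions (section 7.2). Assumed, because the documents do not say: five fractions a week starting on a Monday, or every other day for some SBRT.

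**Course length.** For n fractions at five a week, L = 7 × floor((n - 1)/5) + ((n - 1) mod 5) + 1 calendar days. For n = 33: 7 × 6 + 2 + 1 = 45. For n = 30: 7 × 5 + 4 + 1 = 40.

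**Coverage.** Let the last fraction be day 0, so the course runs from day -(L - 1) to day 0. The look-back runs from day v - 30 to day v. Counting both end days, radiation days covered = max(0, min(L, 31 - v)).

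| Course | L (days) | Visit day 16 | Visit day 30 | Visit day 44 |
|---|---|---|---|---|
| 3 fractions, every other day | 5 | 5 (all) | 1 | 0 |
| 5 fractions, daily | 5 | 5 (all) | 1 | 0 |
| 5 fractions, every other day | 9 | 9 (all) | 1 | 0 |
| 10 fractions | 12 | 12 (all) | 1 | 0 |
| 15 fractions | 19 | 15 (79%) | 1 | 0 |
| 30 fractions | 40 | 15 (38%) | 1 | 0 |
| 33 fractions | 45 | 15 (33%) | 1 | 0 |

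If the boundary day is not counted, 15, 1 and 0 become 14, 0 and 0. The conclusion does not change.

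**When is the whole course covered?** Only if v is at most 31 - L. For L = 5 that means a visit by day 26, for L = 9 by day 22, and for L = 12 by day 19. For L = 19 the limit is day 12, before the earliest permitted visit. For L = 40 and L = 45 it is negative, so no permitted visit covers a 30 to 33 fraction course.

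**Late visits.** At day 44 the look-back starts on day +14, so the Appendix F question also misses days 1 to 13 after radiation. A note beneath the calendar says "FOLLOWUP VISITS AND CT SCANS HAVE A FLEXIBILITY WINDOW OF +/- 8 WEEKS" around the listed time points. If that applied to this visit, the latest day would be 30 + 56 = 86 and the look-back would start on day +56.

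**Controls.** At their nominal visit the same question starts at the end of cycle 2. Cycles 1 and 2 have already been graded under section 6.0, so the short look-back costs them little.

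**The case against.** The strongest reply is that Appendix F does not stand alone.

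- **Appendix J** is due at the same visit and is not capped at 30 days, so its look-back can extend over radiation. This is right, and a reader who took Appendix F for the only scheduled prompt after radiation would be mistaken. But item 3 is confined to delayed complications, which leaves out acute effects during treatment.
- **The calendar row** calls for CTCAE grading of radiation-related toxicity at one month and sets no recall limit. True, but the adverse-event form completed at that visit supplies a limit of 30 days.
- **Recording is mandatory.** A reader might infer that toxicity during radiation goes unrecorded. The documents do not support that. Appendix R requires every adverse event to be entered. It also sends unexpected grade 4 events, unplanned hospitalizations over 24 hours and deaths to the DSMC, both during study treatment and for 30 days after. Severe events are therefore well protected. For lower grades this is a duty to record what is known, not a prompt to ask.
- **Per-cycle grading covers both arms.** Radiation patients are graded at each cycle once immunotherapy resumes, possibly within days of the last fraction. This stands, and it limits the asymmetry to the radiation interval and any wait before resumption. Nor should the whole stretch from enrollment to the last fraction be read as ungraded. Section 3.0 lets maintenance begin before enrollment, so graded cycles may fall in it.
- **Short courses can be covered.** A day-16 visit captures a 3, 5 or 10 fraction course in full, and the longest courses are described for one clinical situation only.
- **No between-arm test of toxicity is planned.** Section 14.2 is descriptive. That lowers the stakes, but descriptive rates still depend on how events are elicited.

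**Conclusion.** The concern holds in a limited form. No toxicity assessment is scheduled during radiation. At the nominal visit or later, the Appendix F question reaches at most the last fraction day. At the earliest permitted visit it covers a short SBRT course but only about 14 to 15 of roughly 40 to 45 days of a 30 to 33 fraction course. Lower-grade acute radiation toxicity that resolves early therefore depends on unprompted reporting, while controls are graded each cycle over the same period. The acute rates reported under objective 2.2.3 and section 14.2 are likely too low in the radiation arm.

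The day counts rest on the assumed fraction schedule. The direction of the under-count is a judgment from the schedule of questions. Its size cannot be estimated, because the documents give neither the number of patients on each course length nor the share of acute events that resolve before the visit. It would be wrong to treat every radiation-arm patient as having missed toxicity.

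**What to change.** Reword the Appendix F question to ask for *any adverse events since the last AE assessment (radiation arm: since the first fraction)*. Add one CTCAE grading to the section 8.1 calendar at the last fraction, a visit the patient already attends. In the same edit, state whether the 14-day or the 8-week window governs the one-month visit.

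The cost is one form line, one calendar entry and a few more adverse event entries, with no new visit and no change to treatment. The reported acute toxicity rate in the radiation arm will be higher than under the present wording, and the report should say that these events were actively elicited.
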